7.1.1 Unanticipated Problem Involving Risk to Subjects or Others (UPIRSO)

Unanticipated problems include any incident, experience, or outcome that meets all of the following criteria:

- Unexpected (in terms of nature, severity, frequency) given (a) the research procedures that are described in the protocol-related documents, such as the Institutional Review Board (IRB) approved

- research protocol and informed consent document; and (b) the characteristics of the subject population being studied;
- Related or possibly related to participation in the research (possibly related means there is a reasonable possibility that the incident, experience, or outcome may have been caused by the procedures involved in the research); and
- Suggests that the research places subjects or others at a greater risk of harm (including physical, psychological, economic, or social harm) than was previously known to an individual or group of individuals (including research subjects, research staff, or others not directly involved in the research).

7.2.2 Reporting to Data and Safety Monitoring Committee (DSMC)

UPIRSOs deemed to be related to the protocol and on-study deaths, including death of a research subject unless the death is expected (e.g. due to disease progression) to be reported to the DSMC within 24 hours of awareness. Hardcopies or electronic versions of the UPIRSO, along with any other supporting documentation available, should be submitted to the DSMC Coordinator. The DSMC Coordinator will forward the information to the DSMC Chair, and/or medical monitor. The DSMC Chair will review all UPIRSOs upon receipt from the DSMC Coordinator and determination of whether the following actions are required: 1) takes action immediately, 2) convenes a special DSMC session (physical or electronic), or 3) defers the action until a regularly scheduled DSMC meeting. Reports are to be emailed to the DSMC team at [contact].

7.2.3 Reporting to the Institutional Review Board (IRB)

The IRB must be notified within 10 business days of “any unanticipated problems involving risk to subjects or others.”

1. Any serious event (injuries, side effects, deaths or other problems), which in the opinion of the PI was unanticipated, involved risk to subjects or others, and has a reasonable possibility of relationship to the research.
2. Any serious accidental or unintentional change to the IRB-approved protocol that alters the level of risk.
3. Any deviation from the protocol taken without prior IRB review to eliminate apparent immediate hazard to a research subject.
4. Any new information (e.g., publication, safety monitoring report, updated sponsor safety report), interim result or other finding that indicates an unexpected change to the risk/benefit ratio for the research.

5. Any breach in confidentiality that may involve risk to the subject or others.
6. Any complaint of a subject that indicates an unanticipated risk or that cannot be resolved by the PI.

8.0 STATISTICAL CONSIDERATIONS

8.1 Sample Size and Randomization

We plan to enroll 16 patients to reach 80% power testing the hypothesis that the proportion of patients with attendance at least 60% of exercise sessions during the initial 6-week period is greater than 50% using an one-sided exact Binomial test at 25% significance level. The actual significance level is 22.7%.

8.2 Data Sets Analyzed

Data from all eligible subjects who have participated in a minimum of 60% of the exercise sessions will be analyzed.

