2.3.8 To assess the impact of a PREHAB program on weight and BMI

2.4 Endpoints**2.4.1 Primary Efficacy Endpoint**

Feasibility – REHAB session feasibility is defined as at least 10 of the 16 participants attending at least 60% of scheduled sessions

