5.6 Subject Replacement

Subjects who withdraw from the study prior to their PREHAB session 1 will be replaced.

Subjects who attend at least the first session will be evaluable for both the primary and secondary endpoint analysis. To be evaluable for exploratory endpoints subjects will need to complete the 3 month follow up visit.

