8.3 Data Analyses/Study Endpoints

Primary Objective: The primary analysis will test the hypothesis of feasibility using an one-sided exact Binomial test at 25% significance level. If 10 or more patients attend a minimum of 60% of exercise sessions during the initial 6-week period, then the study will be declared feasible.

Secondary Endpoints: We will present descriptive measures for secondary endpoints with spaghetti and profile plots for repeated measures

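### Section 8.2 selects the analysis set on the primary outcome and contradicts Sections 2.4.1, 5.6 and 8.1; the count-based feasibility decision survives, but the reported proportion, p-value and exploratory results do not

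*Combined protocol and SAP*

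**What the plan says.** Section 8.2 (Data Sets Analyzed) consists of one sentence: "Data from all eligible subjects who have participated in a minimum of 60% of the exercise sessions will be analyzed". It makes no exception for the primary analysis and does not call the set per-protocol or supportive.

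Other sections describe a different population:

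- Section 2.4.1 defines feasibility as "at least 10 of the 16 participants attending at least 60% of scheduled sessions".
- Section 5.6 states: "Subjects who attend at least the first session will be evaluable for both the primary and secondary endpoint analysis". It also says: "Subjects who withdraw from the study prior to their PREHAB session 1 will be replaced". For the exploratory endpoints it requires completion of the 3-month visit.
- Section 8.1 bases the design on 16 patients, tested "using an one-sided exact Binomial test at 25% significance level", with a null proportion of 50% and an actual level of 22.7%.
- Section 8.3 states: "The primary analysis will test the hypothesis of feasibility using an one-sided exact Binomial test at 25% significance level". It then declares feasibility if 10 or more patients reach 60% attendance; the Study Summary repeats this.
- Section 8.3.1 includes everyone entered at baseline in the safety analysis.

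**The concern.** A feasibility proportion needs a denominator that includes the patients for whom the programme did not work. Section 8.2 removes exactly those patients: anyone below 60% attendance, including those who started and then stopped. Within the remaining set every patient is a success, so the attendance proportion carries no information and neither does a binomial test of it.

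Two results are at stake. The first is the attendance estimate with its p-value or confidence interval, which is the main product of a pilot of this kind. The second is the exploratory material on function, quality of life, sarcopenia, hospitalisation and post-operative course. Under Section 8.2 it would come from adherers only. Under Section 5.6 it would come from 3-month completers. With two competing definitions in the plan, the choice could be made after the data are seen.

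**Working it through.** **Inputs.** n = 16 (Sections 2.4.1 and 8.1); null proportion 0.50 and nominal one-sided level 25% (Section 8.1); decision cut-off of 10 attenders (Sections 2.4.1 and 8.3); analysis set limited to attenders (Section 8.2).

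**Step 1: reproduce the plan's own figure.** For X ~ Binomial(16, 0.5):

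- P(X ≥ 9) = 0.4018
- P(X ≥ 10) = 0.2272
- P(X ≥ 11) = 0.1051

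The stated 22.7% is the value for 10 or more of 16; with 16 patients no other cut-off gives it. The sample-size section therefore assumes that all 16 patients are in the denominator.

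**Step 2: the same test on the Section 8.2 set.** If k of the 16 reach 60%, the set holds k patients, all successes. The proportion is k/k = 100%. The exact one-sided p-value is P(X ≥ k | n = k, 0.5) = 0.5^k, so the possible values are 0.5, 0.25, 0.125 and so on. None of these equals 0.227.

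**Step 3: compare the two sets.**

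| Attenders k | Proportion of 16 | p on 16 | Section 8.2 proportion | p = 0.5^k | Count rule (10 or more) |
|---|---|---|---|---|---|
| 5 | 31.3% | 0.962 | 100% | 0.031 | not feasible |
| 8 | 50.0% | 0.598 | 100% | 0.004 | not feasible |
| 9 | 56.3% | 0.402 | 100% | 0.002 | not feasible |
| 10 | 62.5% | 0.227 | 100% | 0.001 | feasible |
| 12 | 75.0% | 0.038 | 100% | 0.0002 | feasible |

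On 16 patients the test at 25% rejects exactly when k is 10 or more, so test and count rule always agree. On the Section 8.2 set the test rejects from k = 2 (p = 0.25, if equality counts as rejection) or k = 3 (p = 0.125). It then contradicts the count rule for every k from there up to 9.

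**Step 4: exploratory endpoints.** No size can be computed, because the documents give no data linking attendance to outcome. The mechanism can be read from the plan. Sessions can be lost to sickness (Section 5.1.1), blood counts below threshold (Section 6.2.4), or withdrawal and removal (Section 6.6). These plausibly go with poorer health. If exactly 10 of 16 qualify, 16 − 10 = 6 patients drop out of the description.

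**The case against.** The strongest reply is that the plan's decision does not pass through Section 8.2. Feasibility is declared on the number of attenders, and removing non-attenders leaves that number unchanged. Three or eight attenders fall short of 10 under either set. Sections 2.4.1 and 5.6, and the match to 22.7%, show that 16 was the intended denominator. Safety, the only secondary objective, has its own full set. The exploratory endpoints have no hypothesis test, and the direction of any bias is inferred. All of this stands.

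A reader might go further than the documents allow and infer that the trial cannot show infeasibility, or that it would usually be declared feasible when attendance is poor. For example, at a true proportion of 0.25, at least 3 of 16 attend with probability 0.80, and a test on 3 of 3 passes at 25%. That describes a procedure the protocol does not specify, since it sets aside the 10-patient rule, the denominator of 16 and the evaluability rule. Under the stated rule the probability at 0.25 is P(X ≥ 10) = 0.0016.

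The reply does not make Section 8.2 harmless. Section 8.3 specifies a binomial test as well as a count, and on the Section 8.2 set the two can give opposite answers. The count rule protects neither the reported proportion nor the exploratory summaries.

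**Conclusion.** Section 8.2 is circular and contradicts Sections 2.4.1, 5.6 and 8.1. The go/no-go decision on 10 or more attenders is unaffected, and the safety analysis under Section 8.3.1 stays complete. Followed literally, Section 8.2 makes the attendance proportion 100% and the p-value 0.5^k. That means 0.002 against 0.40 with nine attenders, where the test contradicts the count rule, and 0.001 against 0.227 with ten. Exploratory outcomes would be described only in adherers, with a possible bias towards benefit of unknown size.

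This rests on two assumptions. First, 16 patients attend session 1, as the replacement rule in Section 5.6 intends. Second, the operative criterion is the count in the Study Summary and Sections 2.4.1 and 8.3. The Study Schema instead words feasibility as at least half of participants, with no count; that is a separate inconsistency. The correction should be made before analysis, because the attendance estimate is the trial's main result.

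**What to change.** Replace Section 8.2 with three definitions:

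- *Primary:* all eligible subjects who attend at least PREHAB session 1 (Section 5.6). Subjects who withdraw, are removed or are lost stay in the denominator and are classified on the sessions they actually attended out of those scheduled.
- *Safety:* as in Section 8.3.1.
- *Exploratory:* the Section 5.6 evaluable set, not restricted by attendance.

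If the investigators want a set of 60% attenders, label it a supportive adherent subset for exploratory endpoints only. While editing, align the mention of secondary endpoints in Section 5.6 with Section 8.3.1, since the two differ for anyone who leaves between baseline and session 1. Also state how week-7 make-up sessions enter the attendance count, because Section 2.4.1 refers to scheduled sessions and Section 8.3 to the first six weeks.

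The cost is one paragraph of protocol text through the usual amendment route. No new data, visits or patients are needed, and the sample size and the 22.7% level stay as they are.

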8.3 Data Analyses/Study Endpoints

Primary Objective: The primary analysis will test the hypothesis of feasibility using an one-sided exact Binomial test at 25% significance level. If 10 or more patients attend a minimum of 60% of exercise sessions during the initial 6-week period, then the study will be declared feasible.

Secondary Endpoints: We will present descriptive measures for secondary endpoints with spaghetti and profile plots for repeated measures

8.3.1 Safety Analysis

All subjects entered into the study at Baseline will be included in the safety analysis. The frequencies of UPIRSOs by type, body system, severity and relationship to study intervention will be summarized.

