2.4.2 Secondary Efficacy Endpoint

Safety - PREHAB program safety will be evaluated by monitoring unanticipated problems involving risk to subjects or others (UPIRSO). At each PREHAB session, the post intervention evaluation and the 3 month follow up visit the exercise physiologist or personal trainer will record any side effects or symptoms reported by the subject. Within a week the treating physician or Principal Investigator (PI) will review and classify all events. Any events meeting the definition of a UPIRSO will be documented on the UPIRSO log and/or to the IRB by the coordinator within 10 business days.

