6.2.1 Physical Evaluation

- Vitals (Height, Weight, Body Mass Index (BMI))
- Six-minute walk test
- Hand grip strength
- Physical performance metrics
 - Strength is measured in reps within 60 seconds of leg press, bicep curls, heel raises, plank holds and lateral pull downs.
 - Functional testing includes the sit to stand test.
 - Balance testing includes static standing balance with the eyes open and closed on firm and foam surfaces. Balance is rated as poor, fair, good, or excellent.
- Short performance physical battery

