6.5 Time and Events Table

	Screening (Within 28 days of Baseline)	Baseline (Within 14 days of first PREHAB session)	Week 1 – Week 6¹	Post-Intervention Evaluation (Within 14 days of last PREHAB session)	3 Month Follow-Up (± 14 days)
Informed Consent	X				
Confirm Eligibility	X				
Medical History	X				
Demographics	X				
Pregnancy status ²	X				
Godin Leisure-Time Exercise Questionnaire	X				
PAR-Q	X				
Physical Activity Assessment	X				
Vitals (Height, Weight, BMI) ³		X		X	X
Six Minute Walk Test		X		X	X
Hand Grip Strength		X		X	X
Physical Performance Metrics		X		X	X
Short Performance Physical Battery		X		X	X
Unanticipated Problem review			X	X	X
PROMIS-29		X		X	X
PROMIS Cancer 3D Function Profile		X		X	X
SOC Abdomen CT Scan ⁴		X			X
SOC Lab Test Review		X	X ⁵		
Fitbit activity monitoring ⁶		X	X	X	X
Dietitian referral ⁷		X			
Online Pain platform ⁸ Training		X			
Online Pain platform use ⁸			X		
Online Pain platform compliance			X ⁹		
3 x Weekly 1HR PREHAB session			X		
Patient Global Impression of Change ¹⁰				X	
Healthcare Utilization Assessment					X

BMI: Body Mass Index, CT: Computed Tomography, PAR-Q: Physical Activity Readiness Questionnaire

1. Up to 3 missed sessions will be made up in a 7th week
2. Pregnancy status confirmed with patient and via medical record review

3. Height will only be collected at Baseline
4. CT scans completed closest to baseline and 3-month follow-up will be used, even if they occurred outside of the relevant visit window.
5. SOC labs will be reviewed prior to each PREHAB session
6. Fitbit use is only required by those who met eligibility criteria 4.1.9 and do not meet exclusion criteria 4.2.3.
7. Only patients not previously referred to a Dietitian will be referred by the study team
8. Online Pain platform training and use is only required for those who met eligibility criteria 4.1.9 (First 8 participants only)
9. Online Pain platform compliance will be self-reported every 2 weeks (First 8 participants only)
10. Only completed by the participants who used the Online Pain Portal

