7.0 UNANTICIPATED PROBLEMS INVOLVING RISK TO SUBJECTS OR OTHERS (UPIRSO)

7.1 UPIRSO Collection and Reporting

As this trial intervention and the corresponding research procedures pose no known risk to subjects, unexpected/unanticipated problems will be reported in place of Adverse Event reporting. Treating investigator or PI will evaluate patients through medical record review or patient visit from PREHAB session 1 through to the 3 Month Follow-Up visit for any unanticipated problems.

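### The safety analysis set starts at Baseline but problem review starts at session 1, so Baseline exertional testing has no scheduled safety collection and the safety denominator is unsettled

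*Combined protocol and SAP*

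**What the plan says.** Safety is the only secondary endpoint (Sections 2.2 and 2.4.2). The document describes who is analysed for it, and when problems are looked for, in several places.

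**Who is analysed**
- Section 8.3.1: "All subjects entered into the study at Baseline will be included in the safety analysis". The planned summary is: "The frequencies of UPIRSOs by type, body system, severity and relationship to study intervention will be summarized".
- Section 5.6: "Subjects who attend at least the first session will be evaluable for both the primary and secondary endpoint analysis". It also says: "Subjects who withdraw from the study prior to their PREHAB session 1 will be replaced".
- Section 8.2 limits the analysed data to eligible subjects with at least 60% attendance and makes no exception for safety.

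**When problems are looked for**
- Section 7.1: evaluation runs "from PREHAB session 1 through to the 3 Month Follow-Up visit for any unanticipated problems". This review replaces adverse event reporting.
- Section 2.4.2: side effects and symptoms are recorded "At each PREHAB session, the post intervention evaluation and the 3 month follow up visit".
- Section 6.5: the row "Unanticipated Problem review" is marked for Weeks 1 to 6, the post-intervention evaluation and the 3-month visit. Screening and Baseline are blank.

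**What happens at Baseline**
- Section 6.2.1: "Strength is measured in reps within 60 seconds of leg press, bicep curls, heel raises, plank holds and lateral pull downs". The visit also includes a six-minute walk, grip strength, sit-to-stand, balance on firm and foam surfaces, and the short physical performance battery.
- Section 6.2: this takes place up to 14 days before the first session.

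**The concern.** The widest analysis population (8.3.1) includes people for whom nothing is scheduled to detect a problem until they reach session 1. Some of them may never reach it. Baseline testing is the first physical exertion that the research asks of participants, who are selected for low activity (Godin-Shephard score of 23 or less, Section 4.1.4). The definition in Section 7.1.1 covers harm from research procedures generally, so a problem caused by Baseline testing can qualify as a UPIRSO while falling outside the window in 7.1.

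Two things are at stake. First, harms from Baseline testing are not systematically collected, above all in people who withdraw before session 1 and are replaced. Second, the denominator for the only secondary endpoint could be everyone with a Baseline visit, everyone with a first session, or only good attenders, depending on the section followed.

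**Working it through.** **1. The plan's own figures.** No numerical figure is stated for safety, so there is none to reproduce. The one checkable design figure is the actual significance level of 22.7% in Section 8.1. The exact probability of 10 or more successes out of 16 at a true proportion of 0.5 is 0.2272, which agrees. It does not bear on this point, except that 16 is the number of starters used below.

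**2. The passages side by side.**

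| Section | Role | Starting point or requirement |
|---|---|---|
| 8.3.1 | Safety population | Entered at Baseline |
| 5.6 | Evaluable for the secondary endpoint | Attended session 1 (earlier withdrawals replaced) |
| 8.2 | Data analysed | At least 60% of sessions |
| 7.1 | Problem evaluation | From session 1 |
| 2.4.2 | Symptom recording | Sessions, post-intervention, 3 months |
| 6.5 | Scheduled review | Weeks 1 to 6, post-intervention, 3 months |

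The first three rows are populations and differ from one another. The last three are collection windows. They agree with one another but begin later than the 8.3.1 population.

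**3. Same tests, different handling.** Sections 6.3.2 and 6.4.1 repeat the walk, grip, performance metrics and physical battery, and both list a problem review alongside them. Section 6.2 lists the tests without the review. No reason is given.

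**4. Effect of the Baseline denominator.** Inputs: 16 starters (Section 8.1, with replacement under 5.6) and k people who have a Baseline visit but no session 1. The documents do not give k, so a range is assumed. Assume also that every recorded event is among starters and that frequencies are divided by the Baseline count.

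- Dilution factor = 16/(16+k).
- Frequency with one event = 1/(16+k).
- One-sided 95% upper bound with no events = 1 − 0.05^(1/n), where n = 16+k.

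| k (assumed) | n | Factor | One event | Upper bound, no events |
|---|---|---|---|---|
| 0 | 16 | 1.00 | 6.3% | 17.1% |
| 1 | 17 | 0.94 | 5.9% | 16.2% |
| 2 | 18 | 0.89 | 5.6% | 15.3% |
| 4 | 20 | 0.80 | 5.0% | 13.9% |
| 6 | 22 | 0.73 | 4.5% | 12.7% |

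With k = 4 and no events, the upper bound falls from 17.1% to 13.9% although nobody further was under review.

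**5. Effect of Section 8.2 read literally.** Three sessions a week for 6 weeks is 18 sessions, and 0.60 × 18 = 10.8, so 11 sessions are needed. A participant who stopped after 10 sessions, for whatever reason, would be outside the analysed data. If exactly 10 of 16 reach the attendance threshold, which is the smallest result declared feasible, 16 − 10 = 6 starters would be missing from a safety summary built on that set.

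**The case against.** **Unscheduled routes exist.** A reader might infer that a Baseline injury is never reviewed and is lost to oversight. The documents do not support that. Under Section 5.5 the PI is notified of a removal, the reason is recorded and the patient is to be followed up per protocol. Section 6.6.1 permits follow-up after voluntary withdrawal, and the 3-month visit includes problem review. Section 7.2.3 requires IRB notification of UPIRSOs without a start date, and Section 9.5.1 has the PI monitor safety continuously. A starter's Baseline injury could also come to light at session 1. All of this stands. What is missing is scheduled collection, and the other routes depend on someone volunteering or noticing the problem.

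**No denominator is stated.** A reader might infer that non-starters are counted as event-free and that the safety rate is biased downward. Section 8.3.1 promises frequencies without saying what they are divided by or how non-starters are handled, and a table of counts is not diluted. Dilution is therefore conditional.

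**A Baseline strain need not be a UPIRSO.** Section 7.1.1 requires the event to be unexpected, related or possibly related, and suggestive of greater risk than previously known. An ordinary strain may fail the first or third test and add nothing to the tabulated count.

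**The sections might be reconciled.** Section 5.6 excludes non-starters only by implication, and 8.3.1, as the specific safety section, may be meant to govern. Section 9.3 allows registration to be cancelled for a patient who receives no protocol therapy, which could affect who counts as entered. The objective in 2.2.1 concerns the program itself, so a window opening at session 1 is a defensible scope. But if 8.3.1 governs, its population still starts before the review window. If the scope is the program alone, 8.3.1 is too wide. Neither reading removes the mismatch.

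**Conclusion.** The point holds as a mismatch between the safety population and the safety collection window. Baseline exertional testing has no scheduled problem review, and three sections give three different populations for the secondary endpoint. The documents do not establish that the safety rate is biased or that Baseline harms escape oversight.

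The size depends on the number of non-starters, which is not given, and on dividing by the Baseline count, which is not stated. Under those assumptions the dilution is slight for one non-starter (factor 0.94) and noticeable for four (0.80). Safety is descriptive in this 16-person pilot, with no test or threshold attached, and the primary feasibility result does not change. The correction is still worth making: it settles how the only secondary endpoint is reported, and Baseline events that were not collected prospectively may not be recoverable later.

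**What to change.** - Start unanticipated-problem and symptom review at the Baseline physical evaluation: amend 7.1 and 2.4.2, add the review to 6.2, and mark the Baseline column in 6.5.
- Keep the 8.3.1 population for safety, and state that it includes people who are later replaced.
- Limit the session-1 evaluability rule in 5.6 to the primary endpoint.
- State in 8.2 that the 60%-attendance data set does not apply to safety.
- In 8.3.1, report events before session 1 and events from session 1 onward separately, each with its own denominator: those with a Baseline evaluation, and those who attended session 1.

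All of these need to change together. If 2.4.2 or 8.2 is left as it stands, the document will still contradict 8.3.1. The cost is a minor amendment and one log entry per Baseline visit.

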2.2 Secondary Objective

2.2.1 To evaluate the safety of a 6-week supervised PREHAB program for pancreatic cancer patients

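### Safety, the sole secondary objective, is summarised only as UPIRSO frequencies, with no precision, no exposure and no table of the side effects recorded at sessions

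*Combined protocol and SAP*

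**What the plan says.** Section 2.2 of the combined protocol and SAP has a single secondary objective: "To evaluate the safety of a 6-week supervised PREHAB program for pancreatic cancer patients". Section 2.4.2 makes UPIRSO monitoring the endpoint. It adds that at every session, at the post-intervention evaluation and at the 3-month visit "the exercise physiologist or personal trainer will record any side effects or symptoms reported by the subject", and that a physician then reviews and classifies all events.

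The analysis in Section 8.3.1 is one sentence: "The frequencies of UPIRSOs by type, body system, severity and relationship to study intervention will be summarized". Its population is everyone entered at Baseline. Section 8.3 adds only that secondary endpoints will be described, with plots for repeated measures.

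Four other sections bear on this:

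- Section 7.1 uses UPIRSO reporting instead of adverse event reporting, and starts the evaluation at session 1.
- Section 7.1.1 requires three conditions to hold together: the event is unexpected, it is related or possibly related, and it points to greater risk than was known.
- Section 5.6 makes a participant evaluable for the secondary endpoint after one session, and replaces those who withdraw before it.
- Section 8.2 limits analysed data to participants with at least 60% attendance.

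**The concern.** The safety table is built from the event type least likely to occur. Foreseeable problems of supervised exercise, such as the dizziness, lightheadedness and dyspnea for which Section 5.2 makes provision, may well fail the unexpectedness condition and never be counted. The record that would capture them exists but has no place in the analysis.

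With 16 participants, a count of zero or one UPIRSO is compatible with a wide range of true risks, and nothing planned shows that range. Nor does the table show how much exercise the count rests on. Participants may attend anything from 1 to 18 sessions, and sessions can be withheld on laboratory results (Section 6.2.4). A reader could not tell low risk from low exposure. What is at stake is whether the study can say anything quantitative about its only secondary objective.

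**Working it through.** **Inputs from the documents.** N = 16 (Section 8.1). Planned sessions are 3 per week × 6 weeks = 18 per participant (Section 5.1.1), so 16 × 18 = 288 in all. Minimum exposure to be evaluable is 1 session (Section 5.6). The 60% attendance mark is 0.60 × 18 = 10.8, so 11 sessions.

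**Assumption.** The documents give no confidence level for safety. I use 95% and show both one- and two-sided limits.

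1. *The plan's own figure.* No safety figure is stated. The primary rule of 10 or more of 16 against 50% gives P(X ≥ 10) = (8008 + 4368 + 1820 + 560 + 120 + 16 + 1)/65536 = 14893/65536 = 0.227. This matches "The actual significance level is 22.7" per cent and confirms 16 as the working N.

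2. *Zero events in 16.* The exact upper limit is 1 − a^(1/n).
   - One-sided 95%: 1 − 0.05^(1/16) = 17.1%.
   - Two-sided 95%: 1 − 0.025^(1/16) = 20.6%.

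3. *One event in 16.* The limit is a quantile of the Beta(x + 1, n − x) distribution, here Beta(2, 15). It is 26.4% at the 0.95 quantile and 30.2% at the 0.975 quantile.

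4. *Chance of a clean table.* This is (1 − p)^16 for an assumed per-participant risk p. The values of p are illustrative.

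| True risk p | P(zero events in 16) |
|---|---|
| 5% | 44.0% |
| 10% | 18.5% |
| 15% | 7.4% |
| 20% | 2.8% |

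5. *Dependence on N.* Section 8.3.1 counts from Baseline, and withdrawals before session 1 are replaced, so N could exceed 16. The 60% restriction in Section 8.2 could reduce it. The values 20 and 10 below are illustrative.

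| N with zero events | One-sided 95% | Two-sided 95% |
|---|---|---|
| 10 | 25.9% | 30.8% |
| 16 | 17.1% | 20.6% |
| 20 | 13.9% | 16.8% |

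6. *Exposure.* Ten participants at 11 sessions and six at 1 session still pass the feasibility rule, with 10 × 11 + 6 × 1 = 116 sessions, or 116/288 = 40% of plan. With zero events arising at sessions, the one-sided 95% limit per 100 sessions is 1.03 for 288 sessions and 2.55 for 116. These limits treat sessions as independent with constant risk. Sessions within one participant are not independent, so the limits only show direction and rough size.

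**The case against.** The best defence is that this is a single-arm pilot with descriptive safety. The missing interval biases no estimate and alters no decision in the protocol, and any reader could compute the limit from the count and N. Describing secondary endpoints also does not rule out proportions or intervals. That is fair, and it limits the point to a reporting gap. But an exact interval is itself descriptive, and a reader cannot recover untabulated side effects or unreported exposure.

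Three stronger readings are tempting, and the documents do not support them:

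- *That zero events would be declared safe, or carried into a larger trial.* No section sets a safety threshold or decision rule, and none mentions a later trial.
- *That there is no denominator.* There is a head count, namely everyone entered at Baseline. What is missing is exposure.
- *That a poorly attended programme would look the safest.* Attendance is the primary endpoint and would be reported beside safety, and a largely unattended programme fails the 10-of-16 rule. What remains is partial: the 116-session case passes that rule on 40% of planned exposure.

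Attended sessions are also not the whole exposure. Participants are advised to train at home (Section 5.1.3), and UPIRSOs are evaluated through to the 3-month visit (Section 7.1). All UPIRSOs divided by attended sessions would therefore mismatch numerator and denominator. The documents give no per-session risk, so expected event counts cannot be derived from them.

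**Conclusion.** The point holds as a reporting gap that should be closed; the primary test is not affected. As written, the safety analysis yields a probably sparse count of narrowly defined events, without precision or exposure, and leaves the session-level record unused. With 0 of 16, a per-participant risk of up to 17.1% (one-sided 95%) or 20.6% (two-sided 95%) is not excluded; with 1 of 16, the limits are 26.4% and 30.2%.

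These sizes assume exactly 16 analysed participants and a 95% level. The limits shift with N as shown in the working. That few UPIRSOs will occur is a judgement from the definition in Section 7.1.1, not a figure in the documents.

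**What to change.** In Section 8.3.1:

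- Report the number and proportion of participants with at least one UPIRSO and, separately, with at least one recorded side effect or symptom. Give each an exact two-sided 95% confidence interval computed on the actual N.
- Use as denominator those who started session 1, because UPIRSO evaluation begins there. State that the 60% attendance restriction in Section 8.2 does not apply to this table.
- Show total sessions attended and sessions per participant alongside, from the attendance record needed for the primary endpoint.
- If a per-session rate is given, restrict its numerator to events arising at supervised sessions, and note that sessions within a participant are not independent.

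Section 6.2.4 anticipates neoadjuvant therapy during participation, so some recorded symptoms will reflect disease or treatment. In a single arm, their proportion describes what occurred and does not attribute it to the programme.

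The cost is a few extra table lines from data already collected, and a safety statement less favourable than a bare count of zero.
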